### 9.2 Identification of individuals in publications and presentations.

Do you plan to use potentially identifiable information about subjects in publications and presentations, or is it possible that individual identities could be inferred from what you plan to publish or present?

	No
	Yes

→ If yes, will you obtain subject consent for this use?

	Yes
	No

→ If no, describe the steps you will take to protect subjects (or small groups of subjects) from being identifiable.

### 9.3 State mandatory reporting.

Each state has reporting laws that require some types of individuals to report some kinds of abuse, and medical conditions that are under public health surveillance. These include:

- Child abuse
- Abuse, abandonment, neglect, or financial exploitation of a vulnerable adult
- Sexual assault
- Serious physical assault
- Medical conditions subject to mandatory reporting (notification) for public health surveillance

Are you or a member of your research team likely to learn of any of the above events or circumstances while conducting your research **AND** feel obligated to report it to state authorities?

	No
	Yes

→ If yes, the UW IRB expects you to inform subjects of this possibility in the consent form or during the consent process, unless you provide a rationale for not doing so:

**9.4 Retention of identifiers and data.** Check the box below to indicate your assurance that you will not destroy any identifiers (or links between identifiers and data/specimens) and data that are part of your research records until after the end of the applicable records retention requirements (e.g. Washington State; funding agency or sponsor; Food and Drug Administration) for your research. If you think it is important for your specific study to say something about destruction of identifiers (or links to identifiers) in your consent form, state something like “the link between your identifier and the research data will be destroyed after the records retention period required by state and/or federal law.”

*This question can be left blank for conversion applications (existing paper applications that are being “converted” into a Zipline application.)*

*See the “Research Data” sections of the following website for UW Records management for the Washington State research records retention schedules that apply in general to the UW (not involving UW Medicine data):*

<http://f2.washington.edu/fm/recmgt/gs/research?title=R>

*See the “Research Data and Records” information in Section 8 of this document for the retention schedules for UW Medicine Records: <http://www.uwmedicine.org/about/Documents/UWM-Records-Retention-Schedule-v1.6.pdf>*

**Confirm**

**9.5 Certificates of Confidentiality.** Are you planning to obtain a federal Certificate of Confidentiality for your research data? *NOTE: Answer “No” if your study is NIH funded, because all NIH-funded studies automatically have a Certificate.*

**No**  
 **Yes**

**9.6 Data and specimen security protections.** Identify your data classifications and the security protections you will provide, referring to the [ZIPLINE GUIDANCE: Data and Security Protections](#) for the minimum requirements for each data classification level. ***You cannot answer this question without reading this document. Data security protections should not conflict with records retention requirements.***

a. Which level of protections will you apply to your data and specimens? If you will use more than one level, describe which level will apply to which data and which specimens.

Level 1

b. Use this space to provide additional information, details, or to describe protections that do not fit into one of the levels. If there are any protections within the level listed in 9.6.a which you will *not* follow, list those here.

All project data will be stored on a secured server.

## 10 RISK / BENEFIT ASSESSMENT

**10.1** **Anticipated risks.** Describe the reasonably foreseeable risks of harm, discomforts, and hazards to the subjects and others of the research procedures. For each harm, discomfort, or hazard:

- Describe the magnitude, probability, duration, and/or reversibility of the harm, discomfort, or hazard, AND
- Describe how you will manage or reduce the risks. Do not describe data security protections here, these are already described in Question 9.6.
- Consider possible physical, psychological, social, legal, and economic harms, including possible negative effects on financial standing, employability, insurability, educational advancement or reputation. For example, a breach of confidentiality might have these effects.
- Examples of "others": embryo, fetus, or nursing child; family members; a specific group.
- Do not include the risks of non-research procedures that are already being performed.
- If the study design specifies that subjects will be assigned to a specific condition or intervention, then the condition or intervention is a research procedure - even if it is a standard of care.
- Examples of mitigation strategies: inclusion/exclusion criteria; applying appropriate data security measures to prevent unauthorized access to individually identifiable data; coding data; taking blood samples to monitor something that indicates drug toxicity.
- As with all questions on this application, you may refer to uploaded documents.

The only risk associated with the study is a breach of confidentiality. This risk is small because security measures are in place to protect all data. Furthermore, the nature of the data gathered is not sensitive. No additional (e.g. physical) risks to subjects are anticipated. Datasets will use study IDs to further help protect participant confidentiality.

**10.2** **Reproductive risks.** Are there any risks of the study procedures to men and women (who are subjects, or partner of subjects) related to pregnancy, fertility, lactation or effects on a fetus or neonate?

Examples: direct teratogenic effects; possible germline effects; effects on fertility; effects on a woman's ability to continue a pregnancy; effects on future pregnancies.

	No
	Yes

→ If no go to [question 10.3](#)

→ If yes, answer the following questions:

**a. Risks.** Describe the magnitude, probability, duration and/or reversibility of the risks.

**b. Steps to minimize risk.** Describe the specific steps you will take to minimize the magnitude, probability, or duration of these risks.

Examples: inform the subjects about the risks and how to minimize them; require a pregnancy test before and during the study; require subjects to use contraception; advise subjects about banking of sperm and ova.

If you will require the use of contraception: describe the allowable methods and the time period when contraception must be used.

**c. Pregnancy.** Describe what you will do if a subject (or a subject's partner) becomes pregnant

For example; will you require the subject to immediately notify you, so that you can discontinue or modify the study procedures, discuss the risks, and/or provide referrals or counseling?

**10.3 Unforeseeable risks.** Are there any research procedures that may have risks that are currently unforeseeable?

*Example: using a drug that hasn't been used before in this subject population.*

	No
	Yes

→ If yes, identify the procedures.

**10.4 Subjects who will be under regional or general anesthesiology.** Will any research procedures occur while subjects-patients are under general or regional anesthesia, or during the 3 hours preceding general or regional anesthesia (supplied for non-research reasons)?

	No
	Yes

→ If yes, check all the boxes that apply.

Administration of any drug for research purposes

Inserting an intra-venous (central or peripheral) or intra-arterial line for research purposes

Obtaining samples of blood, urine, bone marrow or cerebrospinal fluid for research purposes

Obtaining a research sample from tissue or organs that would not otherwise be removed during surgery

Administration of a radio-isotope for research purposes\*\*

Implantation of an experimental device

Other manipulations or procedures performed solely for research purposes (e.g., experimental liver dialysis, experimental brain stimulation)

If you checked any of the boxes:

You must provide the name and institutional affiliation of a physician anesthesiologist who is a member of your research team or who will serve as a safety consultant about the interactions between your research procedures and the general or regional anesthesia of the subject-patients. If your procedures will be performed at a UW Medicine facility or affiliate, the anesthesiologist must be a UW faculty member.

*\*\* If you checked the box about radio-isotopes: you are responsible for informing in advance all appropriate clinical personnel (e.g., nurses, technicians, anesthesiologists, surgeons) about the administration and use of the radio-isotope, to ensure that any personal safety issues (e.g., pregnancy) can be appropriately addressed. This is a condition of IRB approval.*

**10.5 Data and Safety Monitoring.** A Data and Safety Monitoring Plan (DSMP) is required for clinical trials (as defined by NIH). If required for your research, upload your DSMP to the **Supporting Documents** SmartForm in **Zipline**. If it is embedded in another document you are uploading (for example, a Study Protocol, use the text box below to name the document that has the DSMP.

N/A

**10.6 Un-blinding.** If this is a double-blinded or single-blinded study in which the participant and/or you do not know the group to which the participant is assigned: describe the circumstances under which un-blinding would be necessary, and to whom the un-blinded information would be provided.

N/A

**10.7 Withdrawal of participants.** If applicable, describe the anticipated circumstances under which participants will be withdrawn from the research without their consent. Also, describe any procedures for orderly withdrawal of a participant, regardless of the reason, including whether it will involve partial withdrawal from procedures and any intervention but continued data collection or long-term follow-up.

N/A

**10.8 Anticipated direct benefits to participants.** If there are any direct research-related benefits that some or all individual participants are likely to experience from taking part in the research, describe them below:

*Do not include benefits to society or others, and do not include subject payment (if any). Examples: medical benefits such as laboratory tests (if subjects receive the results); psychological resources made available to participants; training or education that is provided.*

Aim 1:  
[redacted]

Aims 2/3:

A potential benefit to local health departments is increased capacity to do worksite wellness activities. Worksites and their workers will potentially benefit from this research by creating healthier environments for their workers.

**10.9 Individual subjects findings.**

a. Is it likely that your research will unintentionally discover a previously unknown condition such as a disease, suicidal intentions, or genetic predisposition?

No  
 Yes

→ If yes, explain whether and how you would share the information with the subject.

      No  
       Yes → If yes, complete and upload the [SUPPLEMENT: Participant Results Sharing](#) to the Supporting Documents SmartForm of **Zipline**

b. Do you plan to share the individual results of any of your study procedures or findings with the subjects – such as genetic test results, laboratory tests, etc.?

*You should answer YES if your consent form says anything about sharing individual information with subjects.*

No  
 Yes → If yes, complete and upload the [SUPPLEMENT: Participant Results Sharing](#) to the Supporting Documents SmartForm of **Zipline**

**10.10 Commercial products or patents.** Is it possible that a commercial product or patent could result from this study?

No  
 Yes → If yes, describe whether subjects might receive any remuneration/compensation and, if yes, how the amount will be determined.

## 11 ECONOMIC BURDEN TO PARTICIPANTS

**11.1 Financial responsibility for research-related injuries.** Answer this question only if the lead researcher is not a UW student, staff member, or faculty member whose primary paid appointment is at the UW.

Describe who will be financially responsible for research-related injuries experienced by subjects, and any limitations. Describe the process (if any) by which participants may obtain treatment/compensation.

N/A

**11.2 Costs to subjects.** Describe any research-related costs for which subjects and/or their health insurance may be responsible (examples might include: CT scan required for research eligibility screening; co-pays; surgical costs when a subject is randomized to a specific procedure; cost of a device; travel and parking expenses that will not be reimbursed).

Aims 2/3:

Local health department staff will be responsible for costs related to travel (e.g. going to meet with a worksite) and printing materials for worksites (e.g. *Connect to Wellness* intervention toolkits).

**11.3 Reimbursement for costs.** Describe any costs to subjects that will be reimbursed (such as travel expenses).

Aims 2/3:

Local health department staff will not be reimbursed for any costs.

## 12 RESOURCES

**12.1 Faculty Advisor.** (For researchers who are students, fellows, or post-docs.) Provide the following information about your faculty advisor.

- Advisor's name
- Your relationship with your advisor (for example: graduate advisor; course instructor)
- Your plans for communication/consultation with your advisor about progress, problems, and changes.

N/A

**12.2 Study team communication.** Describe how you will ensure that each study team member is adequately trained and informed about the research procedures and requirements (including any changes) as well as their research-related duties and functions.

**There is no study team.**

All of the investigators on the study team have been trained on IRB, and we will ensure that all study staff have up to date training prior to contacting any participants. The study team will meet at least every other week throughout the project. Study materials will be stored on a shared drive to ensure that all members have ready access to the latest protocols, instruments, and other project-related materials.

## 13 OTHER APPROVALS, PERMISSIONS, and REGULATORY ISSUES

**13.1 Other regulatory approvals.** Identify any other regulatory approvals that are required for this research, by checking applicable boxes

*Do not attach the approvals unless requested by the IRB.*

Approval	Research for which this is required
 Radiation Safety	Procedures involving the use of radioactive materials or an ionizing radiation producing machine radiation, if they are conducted for research rather than clinical purposes. Approvals need to be attached to the Supporting Documents page in Zipline .
 Institutional Biosafety	Procedures involving the transfer/administration of recombinant DNA, DNA/RNA derived from recombinant DNA, or synthetic DNA.
 RDRC	Procedures involving a radioactive drug or biological product that is not approved by the FDA for the research purpose and that is being used without an IND, for basic science research (not to determine safety and effectiveness, or for immediate therapeutic or diagnostic purposes).
 ESCRO	Procedures involving the use of some types of human embryonic stem cells.

**13.2 Approvals and permissions.** Identify any other approvals or permissions that will be obtained. For example: from a school, external site/organization, funding agency, employee union, UW Medicine clinical unit.

*Do not attach the approvals and permissions unless requested by the IRB.*

N/A

**13.3 Financial Conflict of Interest.** Does any member of the team have a Financial Conflict of Interest (FCOI) in this research, as defined by [UW policy GIM 10](#)?

No  
 Yes

→ If yes, upload the Conflict Management Plan for every team member who has a FCOI with respect to this research, to the **Supporting Documents** page of **Zipline**. If it is not yet available, use the text box to describe whether the Significant Financial Interest has been disclosed already to the UW Office of Research.

Study Identification

Unique protocol identification number: STUDY00004627

Brief Title: Training LHD's to disseminate evidence-based interventions to small work sites

Official Title: Training Local Health Departments to Disseminate Evidence-Based Interventions to Small and Low-Wage Worksites

Secondary IDs: 2R01CA160217 [U.S. NIH Grant/Contract Award Number]
NCI-2021-02876 [Registry ID: CTRP (Clinical Trial Reporting Program)]
RG1121453 [Fred Hutch/University of Washington Cancer Consortium]

Document date: June 28th, 2017

This document includes the statistical analysis plan excerpted from our grant proposal. We completed this text on the above date.

Statistical analysis plan

To test whether LHDs in the enhanced arm recruit more worksites than LHDs in the standard arm, we will use a generalized linear model with log link. Robust standard error will be performed to obtain valid test results, since we expect the number of worksites recruited to be overdispersed relative to the Poisson distribution. We will perform a secondary analysis to test whether the rate of recruitment increases over time and whether such an increase is modified by treatment status. To study the time effects, we will analyze the number of worksite recruitments in 6-month intervals. The estimation will be implemented using a generalized estimating equation with an autoregressive working correlation matrix of order 1. Robust standard error will be performed to obtain valid test results of correlated outcome data. We will use linear models to study the worksite implementation score. Since worksites are nested within LHDs, we will implement the estimation using generalized estimating equation with robust standard error.

Power analysis. Our first primary outcome is the number of worksites recruited by each LHD during the study period (24 months). Based on power analysis using the Washington State pilot data, we propose a sample size of 40 LHDs (20 per arm) for this study. The mean number of worksites recruited over a 12-month period was 8.4 (sd=4.4). The proposed design will have at least 80% power to detect a mean difference of 2.6 worksites per year between the two arms. Our second primary outcome is the worksite implementation score, collected 12 months after the initial delivery of *Connect to Wellness*. Based on the preliminary results of the parent project, our design has at least 80% power to detect a 6% difference in implementation scores between the two intervention groups.

Implementation cost analyses. We will assess the overall costs to implement the basic and enhanced training and TA strategies, including all training and TA activities conducted by the research team as well as *Connect to Wellness* activities performed by LHDs. We anticipate five categories of costs: 1) LHD staff time; 2) LHD-incurred costs for printing *Connect to Wellness* materials and traveling to worksites; 3) fixed costs of updating and maintaining the *Connect to Wellness* training materials and website; 4) research staff time to provide training and TA; and 5) ongoing evaluation and communication activities. LHD staff activities will be assessed by multiple approaches. Each LHD will be asked to identify a dedicated amount of time to the intervention for specific staff members, which will be updated quarterly through staff logs using zerosum methodology in which categories of activities must sum to 100% of total hours worked. To ensure generalizability, staff time will be costed from national wage information based on the LHD employees' job titles and years of experience. Research team activities will include staff and resources dedicated to start-up and ongoing training and TA costs. Only costs necessary for *Connect to Wellness* training and TA will be included; costs will not include research activities such as grant administration, human subjects documentation and reporting, and manuscript preparation. We will report all costs in 2020 U.S. dollars.

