## 5 PROCEDURES

**5.1 Study procedures.** Using lay language, provide a complete description of the study procedures, including the sequence, intervention or manipulation (if any), drug dosing information (if any), use of records, time required, and setting/location. If it is available and you think it would be helpful to the IRB: Upload a study flow sheet or table to the **Supporting Documents SmartForm** in **Zipline**.

*For studies comparing standards of care: It is important to accurately identify the research procedures. See UW IRB [POLICY: Risks of Harm from Standard Care](#) and the draft guidance from the federal Office of Human Research Protections, ["Guidance on Disclosing Reasonably Foreseeable Risks in Research Evaluating Standards of Care"](#), October 20, 2014.*

Aim 1:  
[redacted]

Aim 2:

Once a local health department has been recruited to participate in the study, they will be randomized to one of two conditions for the trial: 1) standard training and technical assistance or 2) standard training plus enhanced technical assistance.

Briefly, local health department staff will be trained to deliver the *Connect to Wellness* intervention to worksites that they recruit. In the Assessment phase, staff will measure current worksite implementation of physical activity, nutrition, cancer screening, and tobacco cessation evidence-based interventions (with the Baseline Employer Assessment Survey). [redacted] During the Implementation phase (months 3-12), the worksite begins adopting the recommended evidence-based intervention policies and programs and promoting them to workers. At the conclusion of the Implementation phase (month 12), the local health department staff will re-administer the Employer Assessment Survey. After this 12-month period, worksites are able to contact the local health department for technical assistance; the health department may also periodically contact worksites with study updates or to provide relevant materials or offer implementation support.

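### The SAP does not say whether or how the baseline survey enters the analysis of the second primary outcome, the month-12 worksite implementation score

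*SAP*

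**What the plan says.** The SAP describes itself as an extract: "This document includes the statistical analysis plan excerpted from our grant proposal". Under Power analysis it defines the outcome at a single time point: "Our second primary outcome is the worksite implementation score, collected 12 months after the initial delivery of" the intervention. The analysis takes two sentences: "We will use linear models to study the worksite implementation score", and then "Since worksites are nested within LHDs, we will implement the estimation using generalized estimating equation with robust standard error". No baseline score, change score or other covariate is named. The working correlation for this outcome is not given either; the autoregressive structure belongs to the recruitment analysis. The power statement is that "our design has at least 80% power to detect a 6% difference in implementation scores between the two intervention groups", based on preliminary results of the parent project that are not reproduced.

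Protocol section 5.1 plans two rounds of one instrument. At baseline "staff will measure current worksite implementation of physical activity, nutrition, cancer screening, and tobacco cessation evidence-based interventions (with the Baseline Employer Assessment Survey"), and at month 12 "the local health department staff will re-administer the Employer Assessment Survey". Section 5.2 sends these data to the research team to help decide which strategy is more effective. Both copies of the Protocol form agree on this. Section 5.1 also fixes the order of events: once an LHD joins, "they will be randomized to one of two conditions for the trial"; its staff are then trained and go on to recruit worksites.

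**The concern.** A baseline measurement that appears to be on the same scale as a primary outcome is planned, yet the SAP gives it no role. Three things are at stake.

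- **Starting level.** Randomising LHDs balances LHDs in expectation. It does not ensure balance among worksites that those LHDs recruit later, under different levels of support. A comparison of month-12 scores alone would carry any difference in where the recruited worksites began.
- **Precision.** If baseline and month-12 scores are correlated, the baseline score can reduce the variance of the arm comparison at no data-collection cost.
- **An open choice.** The wording fits a final-score, a baseline-adjusted or a change-score analysis. These can give different answers, and the stated power cannot be tied to any one of them.

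**Working it through.** **1. Can the stated power be reproduced?** No. For this score the documents give no standard deviation, intracluster correlation (ICC), cluster size used, alpha, sidedness or baseline to follow-up correlation. Read 6% as 6 points, take two-sided alpha 0.05 and exactly 80% power with 20 LHDs per arm. The implied SD is then 6 / [(1.960 + 0.842) × √(2/n_eff)], with n_eff = 20m / [1 + (m − 1) × ICC] and m worksites per LHD. For m = 15 this is 26.2, 20.1, 16.9 or 13.5 points at ICC 0, 0.05, 0.10 or 0.20; for m = 5 it is 15.1, 13.8, 12.8 or 11.3. The figure can be neither confirmed nor refuted.

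**2. Implied standard error.** Under the same reading, SE = 6 / (1.960 + 0.842) = 2.14 points. The remaining steps need only this and assumed correlations.

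**3. Same correlation r at worksite and LHD level.** Baseline adjustment multiplies the variance by 1 − r², and power = Φ(6/SE − 1.96).

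| r | 1 − r² | Adjusted SE if 2.14 is unadjusted | Power with baseline | Unadjusted SE if 2.14 is adjusted | Power without baseline |
|---|---|---|---|---|---|
| 0.3 | 0.91 | 2.04 | 84% | 2.25 | 76% |
| 0.5 | 0.75 | 1.85 | 90% | 2.47 | 68% |
| 0.7 | 0.51 | 1.53 | 98% | 3.00 | 52% |

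**4. Different correlations at the two levels.** Assume ICC 0.10 at both times, equal variances, within-LHD correlation 0.5 and between-LHD correlation rb. Use the pooled slope b = 0.1·rb + 0.9 × 0.5. The variance factor is

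[0.1(1 + b² − 2b·rb) + (0.9/m)(1 + b² − b)] / (0.1 + 0.9/m).

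For example, with m = 15 and rb = 0: b = 0.45, and the factor is (0.1 × 1.2025 + 0.06 × 0.7525) / 0.16 = 1.034.

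| m | rb | Factor | Power with baseline, if 80% was unadjusted | Power without baseline, if 80% was adjusted |
|---|---|---|---|---|
| 15 | 0.2 | 0.927 | 83% | 77% |
| 15 | 0 | 1.034 | 79% | 81% |
| 8 | 0.2 | 0.884 | 85% | 75% |
| 8 | 0 | 0.964 | 81% | 79% |

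The last column uses SE = 2.14/√factor. Fifteen is the recruitment expectation per LHD over 24 months (Protocol 2.2). The study period is also 24 months (Protocol 5.1), so fewer worksites may reach month 12; eight is an assumed smaller number.

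**5. Change score, for comparison.** Its variance factor is 2(1 − r). If 6 points is detectable with the unadjusted final score, the change score detects 6√[2(1 − r)] = 7.1, 6.0 or 4.6 points at r = 0.3, 0.5 or 0.7. The baseline-adjusted model detects 6√(1 − r²) = 5.7, 5.2 or 4.3.

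**The case against.** The strongest reply is that this is silence in an extract from a grant proposal. Linear models neither include nor exclude covariates, and the power inputs lie in a parent project outside these documents. That stands. A reader might infer that the SAP has chosen an unadjusted analysis, but the text supports only that the role of baseline is unspecified.

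The link from survey to score is also an inference. Content and month-12 timing match, but no sentence states it. That stands too, and makes the remedy conditional.

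Third, the trial compares implementation strategies. A month-12 comparison that includes which worksites each strategy brings in is a defensible target. Moreover, the worksite baseline is measured after randomisation by LHD staff who know what support they receive. Both points are fair. They are reasons to keep the unadjusted result in view and to state the limits of adjustment; they are not reasons to leave the primary model open.

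Finally, a reader might infer that the trial is underpowered or that the unadjusted comparison is invalid. Neither follows. The SAP claims 80% power or more, so a modest loss need not fall below its claim, and with between-LHD correlation near zero the model without baseline can do as well or slightly better. Omitting the covariate does not invalidate the GEE test, and no part of the documents predicts an imbalance between arms.

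**Conclusion.** The point holds as a gap in prespecification that is cheap to close. For a primary outcome, the SAP leaves unsaid whether and how a planned baseline measurement is used, in a design where worksites are recruited after their LHD is randomised.

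The size is illustrative. It rests on 6% meaning 6 points, two-sided 0.05, power of exactly 80%, and correlations that the documents do not supply. If the 80% was unadjusted, adding baseline moves power to between about 79% and 98% in the cases tried, so the gain may be substantial or absent. If the 80% already assumed adjustment, a model without baseline could have less than the stated power, from about 52% to 81%; the largest losses come from assuming a high correlation at both levels. Any shift from differing starting levels could be zero and cannot be sized from the documents.

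**What to change.** - State how the implementation score is derived and whether a baseline version of the same score exists.
- If it does, prespecify the primary model as month-12 score = arm + that worksite's baseline score, by GEE clustered on LHD with robust standard errors.
- Report baseline scores, and the number missing, by arm.
- Keep the model without baseline as a sensitivity analysis, noting that it includes any effect of which worksites each arm recruited.
- State whether the 80% power figure assumed baseline adjustment.

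The cost is SAP wording and one covariate from a survey already planned. Two limits should be written down. Because baseline is measured after randomisation by LHD staff who know their level of support, adjustment removes only the measured part of an imbalance. And precision may be unchanged or slightly worse if the between-LHD correlation is near zero.
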